**Efficacy of Tranexamic Acid in preventing post operative
blood loss and associated complications in bone
sarcoma patients treated with limb salvage surgery: A
randomized controlled trial.**

IRB# IRB-22-07

DATE OF DOCUMENT: 06-04-2022

STUDY PROTOCOL

Efficacy of Tranexamic Acid in preventing post operative blood loss and associated complications in bone sarcoma patients treated with limb salvage surgery: A randomized controlled trial.

Introduction:

Limb salvage surgery for malignant bone tumors results in extensive bone and soft tissue resection which leads to massive bleeding and requiring a large number of transfusions [1] [2]. Blood transfusions have their own complications like hemolytic reaction, graft versus host disease, the spread of infection and sometime can lead to mortality [3]. Blood loss and related complications may lead to high risk of reoperation, an increased hospital stay, and increases burden over the health resources especially among anemic cancer patients [4].

Tranexamic acid (TXA) is a synthetic analog of lysine that prevents fibrinolysis by blocking the lysine binding sites on plasminogen and it has been extensively used over the past decade in orthopedic surgeries to decrease perioperative blood loss and the transfusion rate [5][6]. Perioperative use of TXA has been shown to reduce intraoperative and postoperative blood loss and to decrease transfusion rates in both total knee arthroplasty and total hip arthroplasty [7][8]. Furthermore, it results in higher postoperative hemoglobin, decreased postoperative pain, swelling, length of hospital stays, and higher patient satisfaction [9][10].

Although there is a long-standing concern about TXA-induced hypercoagulability that may increase the risk for postoperative venous thromboembolism (VTE), there are multiple studies even in high-risk patients supporting its safe use [3][11]. In a review of more than 1,000 patients, 240 of which had multiple risk factors for embolic disease including known prothrombotic conditions, those who received TXA had no additional thrombotic events [12]. In addition, two studies have documented an overall reduction in healthcare costs due to fewer transfusions.[11][13].

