Despite ample research documenting the safety and efficacy of perioperative TXA in patients undergoing arthroplasty, there is no known clinical trial focusing on TXA's use in musculoskeletal oncology patients undergoing endoprosthesis reconstruction. Nonetheless, TXA is used within the musculoskeletal oncology community, with its use varying from surgeon to surgeon. Surgeons who use TXA do so with the intent of limiting perioperative blood loss and transfusion rates in these high blood-loss procedures. However, without clinical trial to support its use in this cohort, these patients, who tend to have an increased number of comorbidities, could be inheriting an increased risk of perioperative complication without the benefits documented. Conversely, patients within this cohort that do not receive TXA could be missing out on the clinical benefits of TXA seen in patients undergoing arthroplasty. This randomized clinical trial will determine the efficacy of tranexamic acid in musculoskeletal oncology population who underwent wide local excision and reconstruction with endoprosthesis and will result in the formation of a guideline about its efficacy in reducing blood loss and adverse events that can be resulted by the use of tranexamic acid in the musculoskeletal oncology population.

Objectives:

To determine the efficacy of tranexamic acid in musculoskeletal tumor who underwent wide local excision and reconstruction with endoprosthesis and determine adverse events that can be resulted by the use of tranexamic acid.

Primary outcome measures:

Blood loss in a surgical patient can be monitored by:

- Drop-in hemoglobin in 72 hours
- The number of transfused PRBC unit
- 72-hour total blood loss as calculated by hemoglobin balance method

Hemoglobin balance method:

The Hemoglobin - balance method is based on the balance of Hemoglobin during the perioperative period of surgery. It is regarded as an important method with intuitive expressiveness and high accuracy and often addresses contemporary clinical issues [14]

$Hb_{\text{loss total}} = BV \times (Hb_i - Hb_e) \times 0.001 + Hb_t$	$Hb_{\text{loss total}}$ (g): The loss volume of Hb
$V_{\text{loss total}} = 1000 \times Hb_{\text{loss total}} / Hb_i$	Hb_i (g/L): The Hb value before surgery
Generally, 1 U banked blood is considered to contain 52 ± 5.4 g Hb[5]	Hb_e (g/L): The Hb value after surgery;
	Hb_t (g): The total volume of blood transfusion

Secondary outcome measures:

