- Thromboembolic events: to be observed over six weeks from the date of surgery
- Hospital stay
- drain output till 72 hours

Methodology

Study Design: A Randomized control trial (RCT)

Setting: Department of surgical oncology, Shaukat Khanum Memorial Cancer Hospital and Research Center, Lahore.

Sample size:

Sample size was calculated on the basis of previous study published by Haase, Douglas R. in 2020. Mean post-operative blood loss in TXA group and non TXA were 981 ± 290 mL and 1542 ± 394 mL, respectively. [02] At 80% power, 95% confidence interval, assuming 10% drop out rate, a total of 36 patients included in this study divided into two groups (18 in each group, TXA versus non TXA) would be required in this study.

Sample selection:**Inclusion criteria:**

Patients with primary or metastatic bone tumors who underwent a resection and an endo-prosthetic reconstruction of the proximal femur, distal femur, proximal tibia and proximal humerus. All patients will be tested for liver function using PT (INR), renal function by serum creatinine and Marrow function by CBC

Exclusion Criteria:

- Patient with a congenital or acquired coagulopathy
- Severe renal or liver insufficiency
- Previous thromboembolic condition
- A patient who received perioperative plasma product
- Pelvic tumor
- Patient who is taking anti-coagulant before surgery
- Patient allergic to tranexamic acid

Enrollment duration: Being a dedicated cancer center, a large number (30-40 per year) of Limb salvage surgeries are performed at Shaukat Khanum Memorial Cancer Hospital. The above-given sample size can therefore be achieved in 10 months.

Dose of tranexamic Acid: A single dose of tranexamic acid will be given intravenously at time of induction according to body weight i.e., 15 mg/kg

Anti-coagulation Protocol: All limb salvage patients started on anticoagulant Injection Enoxaprin subcutaneously after 24 hours of surgery according to body weight i.e. 1.5 mg/kg. Enoxaprin converted to oral tablet Aspirin 75 mg on discharge for 4 weeks.

Study Duration: 12 months after the start of enrollment.

In house admission: Limb salvage surgery patients remain admitted on the floor for an average of 5 days

Follow up Schedule: Physical follow up in clinic 2 weeks after surgery (as per institutional guidelines) and a second follow up at 4 weeks after surgery

Randomization: Intraoperative randomization, patients would be allocated to either of the groups by selecting names from sealed envelopes.

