- Femur _____
- Tibia _____
- Other

Group:

- Tranexamic Acid Given
- Tranexamic Acid Not Given

Length of Bone Resected _____ **Cm**

Wound Healing: (Satisfactory / Unsatisfactory)

Preoperative Hemoglobin _____gms

Preoperative INR _____

Intraoperative Blood Loss: _____mls

Postoperative Hemoglobin after 24 Hours _____gms

Postoperative Hemoglobin after 72 Hours _____

Number of PRBC Transfused Within 72 Hours of Surgery _____

Blood Loss Calculated By Direct Hemoglobin Method _____

Drain Output in 72 Hours: _____mls

Any Thromboembolic Event: _____

Status of Ambulation:

STATISTICAL ANALYSIS PLAN:

Statistician independently pooled data from each case then conducted statistical analysis using SPSS Descriptive data are presented as mean \pm standard deviation (*SD*). Odds ratio (*OR*) with 95% confidence intervals (*CI*) or mean differences (*MD*) with 95% *CI* were calculated for dichotomous and continuous outcomes, respectively. Numerical and measured data were compared using a *t*-test and χ^2 -test, respectively. An appropriate power and sample size calculator was used to calculate statistical power. The following parameters were used in the calculations: α , probability of a type I error for a two-sided test; P_0 , probability of exposure in controls; N , number of patients; m : ratio of control to experimental subjects; and Ψ , odds ratio of exposure in experimental subjects relative to controls. $P < 0.05$ was considered significant.

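### The uncorrected 72-hour haemoglobin drop is a primary measure of blood loss, but red cells given in the same 72 hours offset it, so it tends to understate a tranexamic acid benefit

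*Combined protocol and SAP*

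**What the plan says.** Under Primary outcome measures, the protocol names three ways of monitoring blood loss and does not rank them: "Drop-in hemoglobin in 72 hours", "The number of transfused PRBC unit" and "72-hour total blood loss as calculated by hemoglobin balance method".

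The formula for the third measure adds a transfusion term to the haemoglobin-drop term. The term is defined as "Hb_t (g): The total volume of blood transfusion", and the conversion is given as "Generally, 1 U banked blood is considered to contain 52 ± 5.4 g Hb". The first measure has no such term.

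The Introduction says that this surgery "leads to massive bleeding and requiring a large number of transfusions". The Proforma has fields for haemoglobin at 24 and 72 hours and for "Number of PRBC Transfused Within 72 Hours of Surgery", so transfusion and the later haemoglobin share one window. The Statistical Analysis Plan offers t-tests, chi-square tests, mean differences and odds ratios. It has no adjustment for transfusion and no rule for haemoglobin values taken after a transfusion. No document states when patients are to be transfused.

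The Sample size section rests on blood loss in mL: "Mean post-operative blood loss in TXA group and non TXA were 981 ± 290 mL and 1542 ± 394 mL". It gives no expected value for the haemoglobin drop.

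**The concern.** In a transfused patient, the 72-hour haemoglobin reflects loss minus replacement. Transfusion happens after randomisation and, in ordinary practice, responds to bleeding. If TXA works, controls lose more blood, receive more units and have their 72-hour value pulled back up. The comparison on the raw drop is then biased towards no effect, and more strongly so the more transfusion TXA avoids. Randomisation and blinding do not remove this, because the offset is a consequence of the treatment effect itself.

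The protocol's own formula accepts that transfused haemoglobin has to be added back. It does so in one primary measure of blood loss and not in another that stands beside it. With no ranking, the trial could report a small or null difference on the raw drop and a clear one on the corrected loss, and nothing in the plan says which describes blood loss.

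**Working it through.** The plan gives no expected value or power for the haemoglobin drop, so it has no figure of its own to reproduce here. The check uses the plan's formula and its blood-loss inputs.

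**Inputs from the documents**
- Mean loss 1542 mL (non-TXA) and 981 mL (TXA); difference 1542 − 981 = 561 mL (Sample size).
- Haemoglobin per unit 52 g, SD 5.4 g, so 46.6 to 57.4 g at one SD (Hemoglobin balance method).
- 18 per arm with 10% dropout: 18 × 0.9 = 16.2, taken as 16 evaluable per arm.

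**Assumptions not in the documents**
- Preoperative haemoglobin (Hb_i) 120 g/L, range 100 to 130.
- Blood volume (BV) 4 L.
- The mL figures are treated as balance-method losses. The Sample size section does not say how they were measured.
- Hb_t is read as grams of transfused haemoglobin, 52 × units, as the formula's units require.

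**Formula.** Solving the protocol's two equations for the drop, with V (the total blood loss) and BV in mL:

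Hb_i − Hb_e = (V × Hb_i − 1000 × Hb_t) / BV

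**Without transfusion**
- Control: 1542 × 0.120 = 185.0 g; 185.0 / 4 = 46.3 g/L.
- TXA: 981 × 0.120 = 117.7 g; 117.7 / 4 = 29.4 g/L.
- Difference: 561 × 0.120 = 67.3 g; 67.3 / 4 = 16.8 g/L.

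**Effect of transfusion**
- One unit offsets 52 / 4 = 13 g/L.
- If controls average one unit more than TXA patients: 16.8 − 13 = 3.8 g/L remains.
- Break-even imbalance: 67.3 / 52 = 1.29 units. BV cancels out of this figure.
- Over Hb_i 100 to 130 g/L: 56.1 / 52 = 1.08 to 72.9 / 52 = 1.40 units.
- Over 46.6 to 57.4 g per unit at 120 g/L: 67.3 / 57.4 = 1.17 to 67.3 / 46.6 = 1.44 units.

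**Simulation.** This used 16 per arm, the plan's mL means and SDs, 52 g per unit, t-tests and 20,000 runs per scenario, with assumed BV 4000 to 4500 mL and Hb_i 110 to 120 g/L (SD 12). The transfusion patterns are illustrations only; the documents give none, and none is proposed here.

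| Assumed pattern | Mean difference in raw drop, g/L | Power of raw drop |
|---|---|---|
| No transfusion | 15.0 to 16.8 at Hb_i 120 | about 98.5% |
| Units given to reach 70 g/L | 6.6 to 11.6 | 42–91% |
| Units given to reach 80 g/L | 2.6 to 7.2 | 9–51% |
| Units given to reach 90 g/L | 0.7 to 3.1 | 3–12% |
| Units given to reach 100 g/L | 0.1 to 0.9 | 2.5–4% |

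When units were instead given by volume lost (one per 350–400 mL beyond 600–800 mL), the mean difference was −1.0 to −5.0 g/L.

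Power of the balance-method loss stayed at about 99% throughout. That matches the roughly 99.3% that 16 per arm gives for the stated mL means and SDs, so it reflects no error in blood volume or unit content.

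**The case against.** The strongest reply is that the same list already contains the remedy. One of the other two primary measures counts units and the other adds them back, so anyone reading the raw drop also sees the transfusion difference and the corrected loss. The sample size rests on mL of blood, not on the drop. This stands, and it confines the defect to one of three measures. It does not say which measure governs when they disagree.

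Second, the size is conditional. The documents give no transfusion criterion, rate or expected imbalance. On the inputs above, the average untransfused control ends at 120 − 46.3 = 73.7 g/L, so under sparing transfusion the masking could be modest. This also stands.

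Third, net haemoglobin at 72 hours under usual care is a legitimate randomised comparison. The Introduction counts a higher postoperative haemoglobin among TXA's benefits. The raw drop also needs neither a blood volume nor an assumed content per unit. These are good reasons to keep reporting it, but they do not make it a sound primary measure of blood loss in transfused patients.

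A reader might go further and infer three things that the documents do not support:
- That the raw drop will show TXA as harmful. Reversal needs controls to receive more haemoglobin than the extra they lost, an average imbalance above about 1.1 to 1.4 units. It appeared in the simulation under volume-driven replacement, but not on average when units were given to reach a haemoglobin level. It is a possibility only.
- That a null raw drop would count as failure of the trial. No decision rule requires each primary measure to succeed.
- That the trial cannot meet its efficacy objective. The balance-method loss can still address it.

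**Conclusion.** The point holds as a bias towards no effect in one of three unranked primary measures. The direction follows from the protocol's own formula once transfusion tracks bleeding. That link is an inference, because no transfusion criterion is given, but it is a reasonable one for surgery that the Introduction expects to need many transfusions.

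On the stated assumptions, one extra control unit hides 13 of 16.8 g/L, or 77% of the difference, and about 1.3 extra units hide all of it. Actual masking could lie anywhere from partial to near-total, depending on practice that the documents do not describe. The figures also depend on the assumed preoperative haemoglobin and, for the values in g/L, on the assumed blood volume.

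**What to change.** Amend Primary outcome measures and the Statistical Analysis Plan, before outcome data by arm are seen, as follows:

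1. Make the 72-hour haemoglobin-balance loss the primary measure of blood loss.
2. Move the uncorrected 72-hour haemoglobin drop to a secondary or descriptive outcome, reported by arm beside the number of PRBC units.
3. State that efficacy on blood loss is not judged on the uncorrected drop.

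Do not add a separate corrected haemoglobin drop. The quantity (Hb_i − Hb_e) + 52 × units / BV, with BV in litres, is the formula's total haemoglobin loss divided by blood volume, so it would largely duplicate the measure in item 1.

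The cost is mainly wording, with no added patients or procedures. The downside is that the primary measure then relies on the assumed 52 g per unit and on a blood volume. The plan does not say how blood volume is derived, and the Proforma has no field for weight or height, so the method and its inputs must be recorded. The balance formula already requires this.

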Type of randomization: Computerized block randomization. This will ensure a similar number of patients in both groups. Patients will have their names written on an envelope with contents of the envelope indicating whether tranexamic acid should be given or not. Only one member of research team will be aware of the contents of the envelope, who will not be present in Operation Theater at the time of surgery and will not take part in data collection. Patient in control group will be given 10 cc of normal saline as as placebo.

Blinding: It will be a triple-blind trial since the patients will be unaware of the group to which they have been randomized. The statistician carrying out data analysis and examiners/interviewers carrying out clinical examinations/interviewing patients will also be unaware of the status of tranexamic acid.

Minimizing Bias: It is not possible to eliminate bias altogether. However, the performance bias of the operating surgeon will be limited by not revealing the contents of the sealed envelope. The interviewer's bias will be limited by ensuring that the interviewer is not aware of tranexamic acid status at the time of the interview and by ensuring a standardized interaction between the patient and interviewer.

Intervention: Surgeon who will carry out Limb salvage surgeries, will be a consultant with > 5-year experience in Limb salvage. A single standardized technique will be used in all of the patients.

There is a difference of opinion about the use of tranexamic acid in surgeons at SKMH and both surgical options are practiced. The trial will therefore pose no additional risks to the patients.

References

- Wei W, Wei B: Comparison of topical and intravenous tranexamic acid on blood loss and transfusion rates in total hip arthroplasty. J Arthroplasty 2014;29:2113-2116

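### Thromboembolic events are to be counted over six weeks from surgery, but no contact or other way of finding them after week 4 is described

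*Combined protocol and SAP*

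**What the plan says.** Under Secondary outcome measures, the protocol sets the window: "Thromboembolic events: to be observed over six weeks from the date of surgery". Under Follow up Schedule it gives the contacts: "Physical follow up in clinic 2 weeks after surgery (as per institutional guidelines) and a second follow up at 4 weeks after surgery". Both are timed from surgery. In house admission gives an average stay of 5 days.

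Blinding says that "examiners/interviewers carrying out clinical examinations/interviewing patients will also be unaware of the status of tranexamic acid", and Minimizing Bias adds "ensuring a standardized interaction between the patient and interviewer". Neither section says when the examinations or interviews take place.

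The Proforma has one open line for any thromboembolic event. It also records the hospital record number and the date of surgery, but has no date of last contact. The Statistical Analysis Plan gives general methods for dichotomous and continuous outcomes and does not mention thromboembolism or its time window.

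The Objectives include the aim to "determine adverse events that can be resulted by the use of tranexamic acid". Thromboembolism is the only adverse event listed as an outcome.

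Three statements bear on timing. Sample size gives "a total of 36 patients included in this study divided into two groups (18 in each group, TXA versus non TXA"). Enrollment duration cites 30 to 40 limb salvage operations a year and concludes "The above-given sample size can therefore be achieved in 10 months". The study period is given as "Study Duration: 12 months after the start of enrollment".

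**The concern.** Two stated rules do not meet. The outcome runs to day 42, while the last follow-up described is at day 28. A patient seen at week 4 and not heard from again has an unknown status for the last two weeks of the window, and the plan does not say how that status is to be learned or reported. If such patients are counted as event-free, the rate reported as a six-week rate is really a four-week rate plus whatever late events reached the hospital.

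The Introduction names venous thromboembolism as the long-standing worry about the drug, and the protocol expects the trial to inform a guideline that covers adverse events. A reader of the results would need to know how many patients were actually followed for the stated period.

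**Working it through.** **Window against schedule**

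- Window: six weeks = 42 days from surgery (Secondary outcome measures).
- Last follow-up described: 4 weeks = day 28 (Follow up Schedule).
- Gap: 42 − 28 = 14 days, and 14/42 = 33% of the window. This is a share of days, not of events.
- The inpatient stay averages 5 days, so it does not fill the gap.
- The rest of the protocol, the Proforma and the Statistical Analysis Plan describe no 6-week visit, telephone call, record review or imaging. The interviews under Blinding and Minimizing Bias have no stated timing.

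**Scale of a single missed event**

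With 18 patients per arm, one missed event lowers that arm's rate by 1/18 = 5.6 percentage points. This reflects the size of the trial. It does not estimate how many events the gap would miss, because the documents give neither an event rate nor the timing of events.

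**Whether a day-42 contact fits the study period**

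Randomization is intraoperative, so enrolment and surgery are taken to fall on the same day. Six weeks is 42/30.44 = 1.38 months.

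1. Taking the stated 10-month enrolment at face value: 10 + 1.38 = 11.38. The last day 42 falls at about month 11.4, inside 12 months.
2. Checking the 10 months against the stated volume, on the favourable assumption that every operation yields an eligible, consenting patient:

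| Operations per year | Months to enrol 36 | Enrolled in 10 months | Last day 42 (month) |
|---|---|---|---|
| 40 | 36/40 × 12 = 10.8 | 40 × 10/12 = 33.3 | 10.8 + 1.38 = 12.2 |
| 30 | 36/30 × 12 = 14.4 | 30 × 10/12 = 25 | 14.4 + 1.38 = 15.8 |

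The stated volume therefore does not reproduce the 10-month figure. Enrolling 36 in 10 months would need 36/10 × 12 = 43.2 operations a year. On the protocol's own volume, the last day 42 falls at about month 12.2 to 15.8, after the stated end of the study. At 30 operations a year, enrolment alone exceeds 12 months, so a day-42 contact is not the only thing straining the timetable.

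**The case against.** Several objections have force.

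- **The protocol does not say that follow-up ends at week 4.** This is correct. It describes a second follow-up at that time and is silent afterwards, and the untimed interviews neither establish nor rule out a week-6 contact. The supportable statement is that no contact after week 4 is described, and the point goes no further.
- **Late events may still come to light.** A patient who returns to the same hospital could be identified from the record number, and the event timed from the date of surgery. But no record review is planned, and one hospital's silence does not show that a patient was event-free.
- **The consequence is not demonstrated.** This stands. The shortfall may be zero. Precision is poor in any case: with no events among 18 patients, the upper limit of a two-sided 95% interval is 1 − 0.025^(1/18) = 18.5%. This limits the severity but does not reconcile the two statements.

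A reader might also infer stronger versions that the documents do not support:

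- **That a third of events would be missed.** The 33% counts days, and nothing is said about when events occur.
- **That the comparison is biased.** The same schedule applies to both arms and the examiners are to be blinded. No difference between arms is shown.
- **That the planned odds ratio fails because every patient must be classed as event or no event.** An odds ratio can be calculated among the patients assessed, and the analysis text is generic. It does not itself conflict with the schedule.
- **That a day-42 call fits comfortably in the study period.** It does so only if the 10-month enrolment is accepted, and the protocol's own surgical volume does not support that figure.

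**Conclusion.** The mismatch is real: a 42-day outcome is paired with follow-up described only to day 28. That leaves 14 days (33% of the window) with no described ascertainment for the only named safety outcome. Followed as written, the plan cannot confirm that a patient last seen at week 4 was event-free at week 6, and a rate presented as six-week could be too low in both arms. The amount cannot be computed from the documents and may be zero. The three primary blood-loss measures do not depend on this window.

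The conclusion rests on reading the follow-up schedule as complete. If a later contact is planned but not written down, adding it to the protocol settles the matter. Severity is minor to moderate: a contradiction in a secondary safety outcome that is cheap to correct.

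**What to change.** Reconcile the outcome window with the follow-up schedule, by one of two routes.

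**Option A: keep six weeks.** Add one telephone contact at or after day 42, made by the blinded interviewers already planned. Report the number assessed to day 42 in each arm, and show patients not reached as not assessed rather than event-free. The cost is about 36 calls. Some patients may not be reached, and the last calls may fall after month 12, so the study duration may need a matching restatement.

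**Option B: keep the two visits.** Restate the outcome as events up to the 4-week visit and label the reported rate accordingly. The cost is one line of text and a safety window shorter by two weeks.

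A last-contact date on the Proforma would help under either option by showing how far each patient was followed, but it is not needed to remove the contradiction. Neither option changes the treatment or the sample size.

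### The stated inputs give about 18 to 20 patients at 80% power, not 36 (which has about 97–99% power), and 36 patients in 10 months does not follow from 30–40 operations a year

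*Combined protocol and SAP*

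**What the plan says.** **Sample size (protocol, Methodology).** The planning values come from one earlier study: "Mean post-operative blood loss in TXA group and non TXA were 981 ± 290 mL and 1542 ± 394 mL, respectively". The conclusion drawn is "At 80% power, 95% confidence interval, assuming 10% drop out rate, a total of 36 patients included in this study divided into two groups", with 18 per group.

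**Outcome.** One of the three primary measures is "72-hour total blood loss as calculated by hemoglobin balance method".

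**SAP.** It plans a t-test, a two-sided type I error and a 0.05 threshold. Its account of the power calculation lists a control-group exposure probability (P0) and an odds ratio of exposure. It gives no value for either, and no means or SDs.

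**Enrolment and timeline (protocol).** Enrollment duration says "a large number (30-40 per year) of Limb salvage surgeries are performed" and infers "The above-given sample size can therefore be achieved in 10 months". Study Duration is "12 months after the start of enrollment". Thromboembolic events, a secondary outcome, are "to be observed over six weeks from the date of surgery". The Follow up Schedule has clinic visits at 2 weeks and "a second follow up at 4 weeks after surgery".

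**The concern.** A reader with the stated means, SDs, power, confidence level and drop-out rate should be able to rebuild 36 and cannot. The standardised difference is very large (about 1.6), and at 80% power a difference of that size needs far fewer patients. The number to be randomised is therefore justified by a power figure that does not belong to it, and the SAP does not supply the missing step.

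The enrolment sentence is presented as a deduction from the annual number of operations, but even the top of the stated range falls short. The practical stake is the timeline: if accrual runs late, either enrolment stops before 36 or the last patients' follow-up falls after the stated end of the study.

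**Working it through.** **Inputs.** From Sample size: means 981 and 1542 mL, SDs 290 and 394 mL, 80% power, 95% confidence, 10% drop-out, 1:1 allocation. From the SAP: t-test, two-sided, 0.05. From the timeline items: 30–40 operations a year, 10 months, 12 months, and 4 or 6 weeks of follow-up.

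**1. Trying to reproduce 36**

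- Difference: 1542 − 981 = 561 mL.
- Pooled SD: √((290² + 394²)/2) = 345.9 mL. Standardised difference: 561/345.9 = 1.62.
- Normal formula, n per group = 2(1.960 + 0.842)² × SD²/561². This gives 5.97 for the pooled SD and 7.74 for SD 394.
- t-test power comes from the noncentral t distribution. Each group is then divided by 0.9 and rounded up.

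| Method | Evaluable per group for 80% power | Total after 10% drop-out |
|---|---|---|
| Normal, pooled SD | 6 | 14 |
| t-test, pooled SD | 8 (power 0.795 at 7, 0.854 at 8) | 18 |
| Normal, SD 394 | 8 | 18 |
| t-test, SD 394 in both groups | 9 (power 0.754 at 8, 0.809 at 9) | 20 |

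The normal approximation is too generous at this size: 6 per group has only 72% power under the t-test. For the planned test the answer is 18 to 20.

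Readings that the documents do not state also fall short. A worst-case allowance for a rank test gives 24 to 26. Splitting alpha over three primary measures (0.05/3) needs 10 to 12 per group, or 24 to 28 in total. With the t-test and pooled SD, 36 is reached at 99% power: 16 per group, 16/0.9 = 17.8, rounded up to 18.

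**2. What 36 delivers**

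After 10% drop-out, 18 × 0.9 = 16.2, so 16 are evaluable per group.

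- Power for 561 mL: 99.3% (pooled SD) or 97.4% (SD 394).
- Difference detectable with 80% power: 354 mL (pooled SD) or 403 mL (SD 394).
- SD at which 16 per group has exactly 80% power for 561 mL: about 548 mL, a value that appears nowhere in the documents.

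**3. Enrolment**

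- Operations in 10 months: 30 × 10/12 = 25; 40 × 10/12 = 33.3.
- Rate needed for 36 in 10 months: 36 × 12/10 = 43.2 a year.
- Months to reach 36 operations: 36/40 × 12 = 10.8; 36/35 × 12 = 12.3; 36/30 × 12 = 14.4.

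All of these assume that every operated patient is eligible and consents. The exclusion list, which includes pelvic tumours, can only lengthen them.

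**4. Study duration**

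Four weeks is 0.92 month and six weeks 1.38 months. Enrolment plus follow-up is then 11.7 to 15.3 months with 4 weeks and 12.2 to 15.8 with six, or about 12 to 16 months in all. If operations arrive as a Poisson process (an assumption) and everyone is enrolled, the chance that 36 patients complete follow-up within 12 months is:

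| Operations a year | 4 weeks | 6 weeks |
|---|---|---|
| 40 | 58% | 48% |
| 35 | 28% | 21% |
| 30 | 7% | 5% |

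**5. If enrolment stopped at 10 months**

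With 25 to 33 enrolled, 11 to 14 per group would be evaluable. Power for 561 mL would be 95% to 98% (89% to 95% at SD 394).

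**The case against.** The strongest reply is that little is at risk. The sample size errs upwards, and even a trial stopped at 25 to 33 patients keeps high power for 561 mL. That stands: on these inputs neither mismatch threatens the blood-loss comparison.

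Four stronger readings are tempting, and the documents do not support them.

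- **The trial is twice as large as it should be and could be cut.** The power figures hold only if the cited SDs for post-operative blood loss carry over to the 72-hour haemoglobin-balance measure, which the documents do not show. There are also three unranked primary measures. The margin may be needed.
- **The 12-month duration cannot be met.** The range of 30–40 a year is rounded, and near 40 the outcome is close to even. A miss is likely over most of the range, but not certain.
- **The six-week observation contradicts the clinic schedule.** The visits at 2 and 4 weeks are physical clinic visits, and events up to six weeks could be captured in another way. The protocol does not say how. That is a gap in ascertainment and a separate point.
- **The odds-ratio parameters are an error to be deleted.** The SAP also plans odds ratios for dichotomous outcomes, and thromboembolic events are one. The list may refer to those. What can be said is that it has no values and cannot explain a sample size based on two means.

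**Conclusion.** Both mismatches hold. Under the planned two-sided t-test the stated inputs need about 18 to 20 patients (14 by the normal approximation), so 36 is roughly double, a gap too wide for rounding or choice of formula to explain. The power that belongs to 36 is about 97–99% for 561 mL, given 16 evaluable per group and the cited SDs. The figure of 99% alone applies only to the pooled SD.

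The 10-month enrolment claim fails by about 3 to 11 patients at the stated rate, before any exclusion or refusal. As a consequence, 12 months for the whole study is unlikely to be enough over most of that rate.

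This should be corrected because a stated power and a stated deduction are contradicted by the protocol's own figures. It is not a finding that the trial is too small.

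**What to change.** 1. **Sample size.** Keep 36 and restate it along these lines: *with 36 enrolled and 16 evaluable per group, two-sided 0.05, power is about 97–99% for 561 mL, and 80% for about 354 mL (pooled SD) to 403 mL (SD 394), provided the cited SDs apply to the 72-hour blood-loss measure.* Give a different derivation only if one was actually made before the trial; assumptions should not be fitted afterwards to reach 36.
2. **SAP.** Add the two-means inputs: 981 ± 290 and 1542 ± 394 mL, two-sided 0.05, power, 1:1 allocation and 10% drop-out. State which outcome and values the P0 and odds-ratio parameters refer to, or remove them if there are none.
3. **Timeline.** Restate expected enrolment as about 11–14 months or longer, before exclusions and refusals. Set the study duration to cover enrolment plus follow-up (about 12–16 months on the same basis) in place of 12.
4. **Separately,** reconcile the six-week thromboembolic observation with the clinic schedule that ends at 4 weeks.

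The cost is wording in the protocol and SAP and a longer stated timeline. No additional patients are needed.
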